2.2. Study Objective(s) and Endpoint(s)

Objectives	Endpoints
Primary Objectives	Primary Endpoints

 To demonstrate the non-inferior antiviral activity of CAB LA + RPV LA every 8 weeks (every two months) compared to CAB LA + RPV LA every 4 weeks (monthly) over 48 weeks in suppressed HIV-1 infected antiretroviral therapy (ART)-experienced participants 	
 Proportion of participants with plasma HIV-RNA greater than or equal to 50 copies/mL as per Food and Drug Administration (FDA) Snapshot algorithm at Week 48 (Intent-to-Treat Exposed [ITT-E] population)
Secondary Objectives	Secondary Endpoints

 To demonstrate the antiviral and immunologic activity of CAB LA + RPV LA every 8 weeks compared to CAB LA + RPV LA every 4 weeks 	
 Proportion of participants with plasma HIV-1 RNA <50 c/mL (c/mL) at Week 24, Week 48 and Week 96 using the FDA Snapshot algorithm (Intent-to-Treat Exposed [ITT-E] population) Proportion of participants with protocol-defined confirmed virologic failure (CVF) through Week 24, Week 48 and Week 96 Proportion of participants with HIV-RNA greater than or equal to 50 c/mL as per FDA Snapshot algorithm at Week 24 and Week 96 Absolute values and changes from Baseline in viral load and CD4+ cell counts over time including Week 48 and Week 96

 To evaluate the safety and tolerability of CAB LA + RPV LA every 8 weeks compared to CAB LA + RPV LA every 4 weeks 	
 Incidence and severity of AEs and laboratory abnormalities over time including Week 24, Week 48 and Week 96 Proportion of participants who discontinue treatment due to AEs over time including Week 24, Week 48 and Week 96

Objectives	Endpoints
	96 
 Change from Baseline in laboratory parameters over time including Week 48 and Week 96

 To assess viral resistance in participants experiencing protocol-defined confirmed virologic failure 	
 Incidence of treatment emergent genotypic and phenotypic resistance to CAB, RPV through Week 24, Week 48 and Week 96

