3.2. Final Analyses

The primary analysis will be conducted to evaluate the primary objective of the protocol at Week 48. These analyses will be performed after the completion of the following sequential steps:

1. All subjects have completed Week 48 and had a re-test for HIV-1 RNA if necessary.
2. All required database cleaning activities have been completed and database release (DBR) and database freeze (DBF) has been declared by Data Management.
3. All criteria for unblinding the randomization codes have been met.
4. Randomization codes have been distributed according to Ramos NG procedures.

Two secondary analyses will be conducted at Week 24 and Week 96 and a final End-of-Study analysis will be conducted when all subjects have completed the study as defined in the protocol.

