15.4. Appendix 4: Study Phases and Treatment State

15.4.1. Study Phases

Assessments and events will be classified according to the time of occurrence relative to the Treatment Start Date defined in Section 15.6.1.

AEs will be assigned to study phases as defined in Table 13. For example, adverse events on/after start of maintenance phase IP and prior to start of Extension phase IP/LTFU ART will be assigned to the Maintenance Phase.

Laboratory data (efficacy, safety, PK and virology), HIV associated Conditions, health outcomes assessments, vital signs, and ECGs will be assigned to study phases as defined as in Table 14. For example, assessments/events occurring after start of maintenance phase IP and up to and including start of extension phase IP/LTFU ART will be assigned to the Maintenance Phase.

Assessments/events are assigned to study phases sequentially, starting from the top of each table. No study phases will be assigned to medications.

Table 13 Assignment of Study Phases for AEs

Study Phase	Definition
Screening	Date < Maintenance Treatment Start Date
Maintenance	
For participants continuing into Extension Phase: Maintenance Treatment Start Date ≤ Date < Date of Nominal Week 100 Visit
 
For participants not continuing into Extension Phase^[a]: Maintenance Treatment Start Date ≤ Date < LTFU ART Start Date For AEs leading to withdrawal and started on the same date as LTFU ART Start Date, Maintenance Phase, instead of Long-term Follow-up phase, will be assigned.

Extension	
Participants continuing into Extension Phase^[a]: Date of Nominal Week 100 Visit ≤ Date < LTFU ART Start Date For AEs leading to withdrawal and started on the same date as LTFU ART Start Date, Extension Phase, instead of Long-term Follow-up phase, will be assigned.

NOTES:

- Date = AE Start date
- [a] If participants have missing LTFU ART start date, only the lower bound will be considered in the derivation.

Table 14 Assignment of Study Phases for Lab Assessments (including PK and Virology), ECG, Protocol Deviations, Vital Sign, Health Outcomes, HIV Associated Conditions

Study Phase	Definition
Screening	Date \leq Maintenance Treatment Start Date Note: 2-hour post-dose ECG taken on the Maintenance Treatment Start Date will be excluded.

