15.14.5.4. Safety Tables

Safety Tables							
No. in W48	No. in W96	No. in EOS	Population	IDSL / Example Shell	Title	Programming Notes	Deliverable
Exposure							
3.1	3.1	3.1	Safety	201585/primary_02/T3.1	Summary of Extent of Exposure to Investigational Product (Maintenance Phase)	No need for the first two footnotes. Update the last footnote to be below: Note: The injection at nominal visit of Week 100 was not included in the summary of Exposure (No. of IP injections).	W48, W96, EOS
NA	3.2	3.2	Safety	201585/primary_02/T3.1	Summary of Extent of Exposure to Investigational Product (Maintenance + Extension Phase)	Remove the footnotes.	W96, EOS
3.2	3.3	NA	Safety	201585/primary_03/T3.102	Summary of Needle Length and Gauge for CAB Injection (Maintenance Phase)	Display both arms.	W48, W96
3.3	3.4	NA	Safety	201585/primary_03/T3.103	Summary of Needle Length and Gauge for RPV Injection (Maintenance Phase)	Display both arms.	W48, W96
3.4	3.5	NA	Safety	201585/primary_02/T3.6	Summary of Adherence to CAB/RPV Injection Dosing Schedule (Maintenance Phase)	Display both arms. Adjust the footnotes as appropriate.	W48, W96
Adverse Events							
3.5	3.6	NA	Safety	201585/primary_02/T3.7	Summary of All Adverse Events by System Organ Class (Maintenance Phase)		W48, W96
3.6	3.7	NA	Safety	201585/primary_02/T3.8	Summary of All Adverse Events by System Organ Class and Maximum Toxicity (Maintenance Phase)		HL, W48, W96

Safety Tables							
No. in W48	No. in W96	No. in EOS	Population	IDSL / Example Shell	Title	Programming Notes	Deliverable
NA	3.8	3.3	Safety	201585/primary_02/T3.8	Summary of All Adverse Events by System Organ Class and Maximum Toxicity (Maintenance + Extension Phase)		W96, EOS
3.7	3.9	NA	Safety	201585/primary_02/T3.8	Summary of All Adverse Events Excluding Study Drug Injection Site Reactions by System Organ Class and Maximum Toxicity (Maintenance Phase)		HL, W48, W96
NA	NA	3.4	Long-term Follow-up	201585/primary_02/T3.8	Summary of All Adverse Events by System Organ Class and Maximum Toxicity (Long-term Follow-up Phase)		EOS
3.8	3.10	NA	Safety	201585/primary_02/T3.11	Summary of All On-treatment Adverse Events by System Organ Class and Maximum Toxicity (Maintenance Phase)		W48, W96
3.9	NA	NA	Oral Lead-in	201585/primary_02/T3.13	Summary of All Adverse Events by System Organ Class and Maximum Toxicity (Oral Lead-in Period during the Maintenance Phase)	Remove the footnote. Display both arms.	W48

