3.21	3.24	NA	Safety	201585/primary_02/T3.30	Summary of Drug-related Non-Fatal Serious Adverse Events by Overall Frequency (Maintenance Phase)		W48, W96
3.22	3.25	NA	Safety	201585/primary_02/T3.31	Summary of Adverse Events Leading to Withdrawal/Permanent Discontinuation of Investigational Product by System Organ Class (Maintenance Phase)		HL, W48, W96
NA	3.26	3.9	Safety	201585/primary_02/T3.31	Summary of Adverse Events Leading to Withdrawal/Permanent Discontinuation of Investigational Product by System Organ Class (Maintenance + Extension Phase)		W96, EOS
3.23	NA	NA	Oral Lead-in	201585/primary_02/T3.34	Summary of Adverse Events Leading to Withdrawal/Permanent Discontinuation of Investigational Product by System Organ Class (Oral Lead-in Period during the Maintenance Phase)	Remove the footnote. Display both arms.	W48
3.24	3.27	NA	Safety	201585/primary_02/T3.35	Summary of Common ($\geq 5\%$) Non-Serious Adverse Events (Maintenance Phase)		W48, W96

Safety Tables							
No. in W48	No. in W96	No. in EOS	Population	IDSL / Example Shell	Title	Programming Notes	Deliverable
3.25	3.28	NA	Safety	201585/primary_02/T3.36	Summary of Subjects and Number of Occurrences of Common (>=5%) Non-Serious Adverse Events by System Organ Class (Maintenance Phase)		W48, W96
3.26	3.29	NA	Safety	201585/primary_02/T3.37	Summary of Subjects and Number of occurrences of SAEs, Fatal SAEs, and Drug-related SAEs (Maintenance Phase)		W48, W96
3.27	3.30	NA	Safety	201585/primary_02/T3.38	Summary of Cumulative Adverse Events by Visit (Maintenance Phase)	Note that this table only display AEs occurring >=5% subjects during Maintenance Phase.	W48, W96
Study Drug Injection Site Reaction Adverse Events (display for both arms)							
3.28	3.31	NA	Safety	201585/primary_02/T3.40	Summary of Study Drug Injection Site Reaction Adverse Events (Event-level Summary) - Maintenance Phase		HL, W48, W96
NA	3.32	3.10	Safety	201585/primary_02/T3.40	Summary of Study Drug Injection Site Reaction Adverse Events (Event-level Summary) - Maintenance + Extension Phase		W96, EOS
3.29	3.33	NA	Safety	201585/primary_02/T3.43	Summary of Subject-level Characteristics of Study Drug Injection Site Reaction Adverse Events – Overall and Common (Maintenance Phase)		W48, W96
NA	3.34	3.11	Safety	201585/primary_02/T3.43	Summary of Subject-level Characteristics of Study Drug Injection Site Reaction Adverse Events – Overall and Common (Maintenance + Extension Phase)		W96, EOS

Safety Tables							

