15.14.5.6. Pharmacokinetic Tables

Note: For WK48 deliverable, data from visits up to Week 48 are included.

Pharmacokinetic Tables							
No. in W48	No. in W96	No. in EOS	Population	IDSL / Example Shell	Title	Programming Notes	Deliverable
4.1	4.1	NA	Pharmacokinetic	201585/primary_02/T4.1	Summary of Plasma CAB PK Concentration (ug/mL) -Time Data by Treatment and Visit – Including Log-transformed Statistics	Remove the first footnote.	W48, W96
4.2	4.2	NA	Pharmacokinetic	201585/primary_02/T4.2	Summary of Plasma RPV PK Concentration (ng/mL) -Time Data by Treatment and Visit – Including Log-transformed Statistics	Remove the first footnote.	W48, W96
4.3	4.3	NA	Pharmacokinetic	201585/primary_02/T4.3	Summary of Evaluable Plasma CAB PK Concentration (ug/mL) -Time Data by Treatment and Visit – Including Log-transformed Statistics	Remove the first footnote.	W48, W96
4.4	4.4	NA	Pharmacokinetic	201585/primary_02/T4.4	Summary of Evaluable Plasma RPV PK Concentration (ng/mL) -Time Data by Treatment and Visit – Including Log-transformed Statistics	Remove the first footnote.	W48, W96
4.5	4.5	NA	Pharmacokinetic	201585/primary_02/T4.3	Summary of Evaluable Plasma CAB PK Concentration (ug/mL) -Time Data by Strata and Treatment and Visit – Including Log-transformed Statistics	Display by rederived randomization strata and add footnote for strata.	W48, W96
4.6	4.6	NA	Pharmacokinetic	201585/primary_02/T4.4	Summary of Evaluable Plasma RPV PK Concentration (ng/mL) -Time Data by Strata and Treatment and Visit – Including Log-transformed Statistics	Display by rederived randomization strata and add footnote for strata.	W48, W96
4.7	4.7	NA	Pharmacokinetic	201585/primary_02/T4.6	Summary of Results of Steady State Assessment by Strata for Q8W Arm- Evaluable Concentration	Display by rederived randomization strata and add footnote for strata. For Q8W arm only.	W48

15.14.5.7. Pharmacokinetic Figures**Note:** Unless otherwise specified, display both arms.

Pharmacokinetic Figures							
No. in W48	No. in W96	No. in EOS	Population	IDSL / Example Shell	Title	Programming Notes	Deliverable
4.1	4.1	NA	Pharmacokinetic	201585/primary_02/ F4.1	Individual Plasma CAB Concentration-Time Plots (Linear and Semi-Log)	Also include prior exposure to CAB+RPV (e.g. 0, 1-24, >24 weeks) for each subject.	W48, W96

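### The main Week 24 and Week 48 AE, SAE and AE-withdrawal tables have no time bound, and only common AEs and injection site reactions get time-indexed incidence

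*SAP*

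**What the plan says.** Section 2.2 lists two secondary safety endpoints that name the analysis weeks: "Incidence and severity of AEs and laboratory abnormalities over time including Week 24, Week 48 and Week 96", and "Proportion of participants who discontinue treatment due to AEs over time including Week 24, Week 48 and Week" 96.

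Section 15.4.1 (Table 13) assigns an AE to the Maintenance Phase. For participants who enter the Extension the window is "Maintenance Treatment Start Date ≤ Date < Date of Nominal Week 100 Visit". For the others it is "Maintenance Treatment Start Date ≤ Date < LTFU ART Start Date", and if that ART date is missing only the lower bound applies. Neither window mentions Week 24 or Week 48.

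Section 3.2 sets the first condition for the Week 48 analysis: "All subjects have completed Week 48 and had a re-test for HIV-1 RNA if necessary". Section 3 treats the Week 24 analysis in the same way, as following completion of that visit by all subjects.

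In section 15.14.5.4 the Week 48 AE table by grade (Table 3.6) is titled "Summary of All Adverse Events by System Organ Class and Maximum Toxicity (Maintenance Phase". The SAE table (3.16) and the table of AEs leading to withdrawal (3.22) are likewise phase-wide. None of the three has a programming note, and the same titles serve the Week 96 report. The Week 24 tables in section 15.14.4.4 (3.1 to 3.5: all AEs, drug-related, Grade 3-5, SAEs, AE withdrawals) have the same form.

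Table 3.27 gives cumulative AEs by visit for the Week 48 and Week 96 reports, with the restriction "Note that this table only display AEs occurring >=5% subjects during Maintenance Phase".

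**The concern.** When the last participant completes Week 48, everyone enrolled earlier has been followed for longer. A phase-wide table taken then gives the proportion with an event over 48 weeks plus a variable extra period. It does not give the proportion by Week 48. A reader who takes the percentage as a 48-week risk will read it too high, and the amount depends on how fast the trial enrolled. The same happens at Week 24. For the rows that readers most need in a safety report (any AE by grade, SAEs, AE discontinuations), the plan lists no clearly bounded version that would deliver the weeks named in section 2.2.

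**Working it through.** The SAP states no figure on this point, so there is none to reproduce. The check has two parts.

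**1. Is a bound implied elsewhere?** The SAP writes a bound where it wants one:
- The PK tables (15.14.5.6) carry the note "For WK48 deliverable, data from visits up to Week 48 are included".
- The cumulative virologic failure table (2.23 in 15.14.5.2) is titled as running up to Week 48 and is paired with an unbounded version (2.24).
- The Week 24 observed-case tables (2.10 and 2.11 in 15.14.4.2) are told to show visits up to Week 24 only.

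The time-to-event rules (15.10) censor participants still in the phase at the data cutoff for the analysis, using last contact date. The SAP therefore expects data beyond the nominal week to be present. The AE, SAE and AE-withdrawal tables have no corresponding note.

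**2. Which displays are time-indexed?**

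| Content | Display | Covers the named weeks? |
|---|---|---|
| AEs in at least 5% of subjects | Table 3.27 | Weeks 24, 48 and 96, but not in the Week 24 report |
| Injection site reactions | Tables 3.30, 3.33, 3.37; Figures 3.6 to 3.11 | By visit, including Grade 3-5 in Figures 3.9 to 3.11 |
| Any AE by grade, all SAEs, other AEs below 5% | None listed | No |
| Discontinuation due to AE | Tables 1.8, 2.3, 2.19 (2.2, 2.8 at Week 24) | Partly; see the objection |

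**Size (illustration only).** The SAP gives neither the enrolment span nor AE rates, so these are assumptions: enrolment uniform over E weeks, constant hazard, no dropout, and a data cut when the last participant reaches Week 48.

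Range for E: section 3.1 intends about half the participants to reach Week 24 before anyone reaches Week 48. Half must then be enrolled in under 48 − 24 = 24 weeks. With uniform accrual the whole span is under about 2 × 24 = 48 weeks. The range used is 13 to 48 weeks, which puts mean follow-up beyond Week 48 at E/2 = 6.5 to 24 weeks.

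Formula: for a true Week 48 incidence p, h = −ln(1 − p)/48. Follow-up is uniform on 48 to 48 + E weeks, which stays below the Week 100 phase end because 48 + 48 = 96. The tabulated incidence is 1 − (1 − p) × (1 − e^(−hE))/(hE).

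Example with p = 5%, E = 48: hE = −ln(0.95) = 0.0513, so 1 − 0.95 × 0.05/0.0513 = 7.4%.

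| True Week 48 incidence | E = 13 | E = 26 | E = 39 | E = 48 |
|---|---|---|---|---|
| 2% | 2.3% | 2.5% | 2.8% | 3.0% |
| 5% | 5.7% | 6.3% | 7.0% | 7.4% |
| 10% | 11.3% | 12.5% | 13.7% | 14.6% |
| 30% | 33.3% | 36.4% | 39.2% | 41.1% |

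At Week 24 the same span is larger relative to follow-up. Only E divided by the named week matters, so E = 13 at Week 24 equals E = 26 at Week 48, and a true 5% becomes 6.3%. At Week 96 the overshoot is small: for participants who enter the Extension, the phase ends at nominal Week 100, about 100 − 96 = 4 weeks later.

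**The case against.** The strongest reply is that much of the endpoint is already delivered. A reader might infer that the plan produces no Week 48 AE incidence at all. It does not support that reading, because Table 3.27 gives it for common AEs and injection site reactions are tabulated and plotted by visit. Section 2.2 also says over time including the named weeks, not at them, and cumulative by-visit displays fit that wording. This part of the reply stands and narrows the point to the rows left uncovered.

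For discontinuations, three kinds of display come close. The Snapshot outcome tables include a category for discontinuation due to AE or death, but a viral load in the window takes precedence and death is combined with AE. The treatment-related Kaplan-Meier tables combine drug-related AE withdrawal with virologic failure and other reasons. Table 1.8 shows withdrawals by visit, but its shell is not at hand, so a split by reason can be neither confirmed nor ruled out. None is clearly the declared proportion.

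The SAP also states no AE extraction rule. That the tables run to the data cut is inferred from the phase definition, the analysis timing and the explicit bounds elsewhere; a rule could exist outside this document. Exposure in participant-years is reported (Table 3.1), which helps a reader allow for unequal follow-up.

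Finally, showing all available safety data at a primary analysis is a legitimate choice. That is a reason to keep the existing tables, not to omit the bounded rows.

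**Conclusion.** The point holds in a limited form. Followed as written, the main Week 24 and Week 48 AE, SAE and AE-withdrawal tables mix unequal follow-up beyond the named week. No listed display clearly bounds any AE by grade, all SAEs, AEs below 5% other than injection site reactions, or the proportion discontinuing due to AEs.

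Under the assumptions above, 5% at Week 48 would appear as about 5.7% to 7.4%, and 10% as about 11.3% to 14.6%. Events concentrated early in treatment, or dropout, would make the excess smaller.

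A reader might also infer that the comparison between arms is biased. The document does not support that: both arms were randomised 1:1 over the same period, so follow-up is extended alike. The effect is mainly on absolute incidence and on reading the reports against each other. This is a worthwhile, inexpensive improvement, and the primary analysis is unaffected.

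**What to change.** Extend the planned cumulative by-visit table (3.27) with rows for any AE, Grade 3-5 AE, drug-related AE, SAE and AE leading to withdrawal, without the 5% filter. Count a participant if onset is on or before the target Study Day of the named week: 7 × 24 + 1 = 169, 7 × 48 + 1 = 337 and 7 × 96 + 1 = 673, as in section 15.3.1 and Table 8. For the withdrawal row, state whether the AE onset date or the discontinuation date decides. Provide the table in the Week 24 report as well, where no by-visit AE table is listed.

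Keep the phase-wide tables and label them as cumulative to the data cut.

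The cost is a little more programming on a table already planned. No new data are needed and no other analysis changes.

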15.14.5.5. Safety Figures

Note: Unless otherwise specified, display both arms.

Safety Figures							
No. in W48	No. in W96	No. in EOS	Population	IDSL / Example Shell	Title	Programming Notes	Deliverable
3.1	3.1	NA	Safety	201585/primary_02/F3.1	Plot of Common Adverse Events and Relative Risk - Q8W vs. Q4W (Maintenance Phase) – Excluding Study Drug ISRs	Remove the second footnote.	HL, W48, W96
3.2	3.2	NA	Safety	201585/primary_02/F3.1	Plot of Common Study Drug Injection Site Reaction Adverse Events and Relative Risk - Q8W vs. Q4W (Maintenance Phase)	Remove the second footnote.	HL, W48, W96
3.3	3.3	NA	Safety	201585/primary_02/F3.5	Plot of Onset, Duration, and Severity of Overall and Common Study Drug Injection Site Reaction AEs by Maximum Grade — CAB and/or RPV (Maintenance Phase)		W48, W96
3.4	3.4	NA	Safety	201585/primary_02/F3.6	Plot of Onset, Duration, and Severity of Overall and Common Drug-related Study Drug Injection Site Reaction AEs by Maximum Grade — CAB (Maintenance Phase)		W48, W96
3.5	3.5	NA	Safety	201585/primary_02/F3.7	Plot of Onset, Duration, and Severity of Overall and Common Drug-related Study Drug Injection Site Reaction AEs by Maximum Grade — RPV (Maintenance Phase)		W48, W96
3.6	3.6	NA	Safety	201585/primary_02/F3.8	Plot of Incidence of Maintenance Phase Study Drug Injection Site Reaction Adverse Events by Visit (Overall and Common) – CAB and/or RPV	Footnote may be adjusted for clarifications.	W48, W96
3.7	3.7	NA	Safety	201585/primary_02/F3.9	Plot of Incidence of Maintenance Phase Drug-Related Study Drug Injection Site Reaction Adverse Events by Visit (Overall and Common) – CAB	Footnote may be adjusted for clarifications.	W48, W96

Safety Figures							
No. in W48	No. in W96	No. in EOS	Population	IDSL / Example Shell	Title	Programming Notes	Deliverable
3.8	3.8	NA	Safety	201585/primary_02/F3.10	Plot of Incidence of Maintenance Phase Drug-Related Study Drug Injection Site Reaction Adverse Events by Visit (Overall and Common) – RPV	Footnote may be adjusted for clarifications.	W48, W96
3.9	3.9	NA	Safety	201585/primary_02/F3.11	Plot of Incidence of Grade 3-5 Maintenance Phase Study Drug Injection Site Reaction Adverse Events by Visit (Overall and Common) - CAB and/or RPV	Footnote may be adjusted for clarifications.	W48, W96
3.10	3.10	NA	Safety	201585/primary_02/F3.12	Plot of Incidence of Grade 3-5 Maintenance Phase Drug-related Study Drug Injection Site Reaction Adverse Events by Visit (Overall and Common) - CAB	Footnote may be adjusted for clarifications.	W48, W96
3.11	3.11	NA	Safety	201585/primary_02/F3.13	Plot of Incidence of Grade 3-5 Maintenance Phase Drug-related Study Drug Injection Site Reaction Adverse Events by Visit (Overall and Common) - RPV	Footnote may be adjusted for clarifications.	W48, W96
3.12	3.12	NA	Safety	201585/primary_02/F3.2	Scatter Plot of Maximum vs. Baseline for ALT (Maintenance Phase)	Display at log10 scale.	HL, W48, W96
3.13	3.13	NA	Safety	201585/primary_02/F3.3	Scatter Plot of Maximum ALT vs. Maximum Total Bilirubin (Maintenance Phase)		HL, W48, W96
3.14	3.14	NA	Safety	201585/primary_02/F3.4	Matrix Plot of Maximum Liver Chemistries during the Maintenance Phase		HL, W48, W96
3.15	3.15	NA	Safety	201585/primary_02/F3.14	Bar Chart of Lipid NCEP Categories at Week 48 vs. Baseline – Triglycerides, Total Cholesterol, LDL Cholesterol	For WK96, replace 'Week 48' with 'Week 96' in the title.	W48, W96
3.16	3.16	NA	Safety	201585/primary_02/F3.15	Bar Chart of Lipid NCEP Categories at Week 48 vs. Baseline - HDL Cholesterol	For WK96, replace 'Week 48' with 'Week 96' in the title.	W48, W96

Safety Figures							
No. in W48	No. in W96	No. in EOS	Population	IDSL / Example Shell	Title	Programming Notes	Deliverable
3.17	3.17	NA	Safety	SAFE_F1	Histogram of Timeliness of Injections (Maintenance Phase)		W48, W96

